7 RISKS AND BENEFITS

7.1 RISK SUMMARY

Risks to the subject have been minimized, but not eliminated. Risks include expected or unexpected toxicity due to treatment with investigational agents, with particular attention towards febrile neutropenia, tumor lysis syndrome, and infusion-related reactions. Anticipated therapy-related toxicities and detailed management plans are found in Section 7.4.

Study associated risks also include vascular injury or bruising associated with venipuncture to obtain the whole blood specimen. Data privacy risks will also be largely limited to rare situations involving possible breach of confidentiality. In this highly unlikely situation, there is a risk that the information, like all medical information, may be misused.

It is necessary for subject-related data (i.e., ethnicity, age, toxicities, etc.) to be re-associated to double coded specimens at the time of data analysis. These subject data will be kept in a separate, secure database. Specimens will be stripped of subject identifiers for downstream analysis. No information concerning results obtained from future biomedical research will be entered into clinical records, nor will it be released to outside persons or agencies, in any way that could be tied to an individual subject.

7.2 LIKELIHOOD OF OCCURRENCE

The risks of therapy-related toxicity are unknown, but based on previously reported early discontinuation rates of 11% with chemotherapy-sparing frontline therapy for FL (Morschhauser et al. 2018), we expect discontinuation rates less than 15% for the three-drug combination. Prior studies of front-line chemotherapy and chemotherapy-sparing agents have reported a rate of 65% for grade 3-4 reactions, and 99% for any grade adverse reaction (Morschhauser et al. 2018). We hypothesize grade 3-4 reactions will occur in fewer than 70% of enrolled patients. The likelihood of vascular injury due to venipuncture is very low. The risk of a data breach from secured, institutionally monitored servers is low.

7.3 POTENTIAL DIRECT BENEFITS TO SUBJECT

The therapeutic benefit to study subjects is unknown. Preclinical experience and the success of combinations of two of the three drugs used in this study in other hematologic malignancies suggests outcomes may be similar or better than existing therapies for FL. If successful, this study may lead to the development and eventual approval of a novel chemotherapy-sparing regimen for the treatment of chronic disease, which can lower the population exposure to chemotoxicity in patients with FL.

7.4 RISKS ASSOCIATED WITH INVESTIGATIONAL AGENTS

Important risks identified in clinical investigations with obinutuzumab were: IRRs, TLS, thrombocytopenia (including acute thrombocytopenia), neutropenia (including prolonged and late onset neutropenia), prolonged B cell depletion, infections (including hepatitis B reactivation and PML), worsening of pre-existing cardiac conditions and GI perforation. See the obinutuzumab IB for additional details.

Based on nonclinical and clinical findings, the potential overlapping toxicities with the addition of venetoclax to obinutuzumab include B cell depletion, neutropenia, and TLS. Given that venetoclax and obinutuzumab target different B-cell subsets and result in an additive pharmacological effect in disease models when combined, it is possible that the rapid, marked depletion of B cells (and total lymphocytes for venetoclax) could lead to increased cases of TLS and infection, and that full reversibility of normal B cells may require a prolonged period without treatment. See the venetoclax IB for additional details.

Oral and intravenous azacitidine has been associated with multilineage cytopenia in preclinical models and clinical trials, particularly neutropenia, through a different mechanism. Studies of the combination of azacitidine and venetoclax in the treatment of myeloid malignancies have highlighted

a risk of febrile neutropenia which is partially abrogated by limiting maximum doses, as has been done in this study. (Jilg et al. 2019). See the azacitidine IB for additional details.

Potential therapy-related risks are described in detail below along with suggested management guidelines.

7.4.1 Tumor Lysis Syndrome

Tumor Lysis Syndrome, or TLS, is a known risk for patients with CLL who are treated with high cell killing agents, including venetoclax or obinutuzumab. TLS can be defined either by laboratory criteria or by clinical criteria following the guidelines of (Howard, Jones, and Pui 2011):

- Two of the following laboratory criteria must be present in serum studies in the same 24-hour window from the time of 3 days prior to therapy until 7 days after initial therapy:
 - \circ Uric acid > 8 mg/dL
 - Phosphorus > 4.5 mg/dL
 - o Potassium > 6 mmol/L
 - Corrected calcium < 7 mg/dL or ionized calcium < 4.5 mg/dL
- One of the following clinical criteria is sufficient to diagnose TLS in the 3 days prior to initial therapy or 7 days after initial therapy:
 - Cardiac dysrhythmia at least probably attributable to hyperkalemia
 - Cardiac dysrhythmia, seizure, neuromuscular irritability, hypotension or heart failure at least probably attributable to hypocalcemia
 - Acute kidney injury, defined by increase in serum creatinine level > 0.3 mg/dL from baseline, a single creatinine value > 1.5x the upper age-adjusted limit of normal, or oliguria defined as < 0.5 mL/kg/hr urine production for at least 6 hours

The risk of TLS is expected to be lower in FL than CLL based on prior studies of each agent individually (Davids et al. 2017; Marcus et al. 2017), but the exact nature of the risk of the combination in FL is unknown. Changes in blood chemistry consistent with TLS that require prompt management can occur as early as 6 to 8 hours following the first dose of venetoclax or obinutuzumab. The risk of TLS exists as a continuum based on multiple factors, including tumor burden and comorbidities. Risk is highest for those with bulky disease, elevated leukocyte count, elevated pretreatment LDH levels, compromised renal function, and dehydration. Perform tumor burden assessment with CT scan and CBC with WBC differential, assess blood chemistry (potassium, uric acid, phosphorus, calcium, and creatinine) in all patients and correct pre-existing chemistry abnormalities prior to initiation of treatment with venetoclax or obinutuzumab.

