4.2.3 Administration Details for Venetoclax for Expansion Cohort

The dosing of venetoclax in this trial assumes the drug will be administered with a meal, and patients will be instructed to take venetoclax immediately prior to a meal. On days when venetoclax is taken with CC-486, venetoclax should be given first.

If vomiting occurs within 15 minutes after taking venetoclax and all expelled tablets are still intact, another dose may be given. Otherwise, no replacement dose is to be given. In cases where a dose of venetoclax is missed or forgotten, the patient should take the dose as soon as possible and ensure that the minimal interval between the current dose and the next dose is at least 16 hours in order to avoid excessive drug accumulation after the next dose.

All patients must receive prophylaxis for tumor lysis syndrome (TLS) with antihyperuricemics (e.g., allopurinol or rasburicase) and ensure adequate hydration prior to start of venetoclax therapy (see Section 7.4.1 and Appendix G for further details). If TLS is diagnosed by laboratory criteria only AND resolves within 48 hours, venetoclax may be resumed at the prior dose without adjustment. If TLS is diagnosed by laboratory criteria AND lasts greater than 48 hours before full resolution OR TLS is diagnosed by clinical criteria, the dose of venetoclax should be reduced following Table 4.

For the purposes of dose adjustment, unacceptable toxicity will be defined as any treatment related AE that is deemed by the treating investigator to be related to venetoclax and/or to the combination of venetoclax with CC-486 and/or obinutuzumab, and that poses a medical risk or substantial discomfort to the subject including, but not limited to, grade 3 or 4 hematologic or non-hematologic toxicity. Treatment should be delayed if there is any evidence of infection until the resolution of any infection-related symptoms. After an episode of unacceptable toxicity resolves or after the first episode of an infectious complication which resolves within 3 weeks, venetoclax may be resumed or re-escalated to the prior dose at the discretion of the treating investigator. After a second or greater episode of an infectious complication which resolves within three weeks, the venetoclax dose should be adjusted as shown in Table 3 and Table 4. Treatment with investigational agents should not be resumed after an infectious complication that remains symptomatic for greater than 3 weeks.

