Anemia ≥ grade 3	 For first instance of grade 3 and 4 anemia, transfuse PRBC's as required If recurs, hold treatment and evaluate etiology (drug-related or not). If drug-related, 	Monitor CBC weekly. No more than 3 dose reductions are allowed If treatment is delayed by more than 6 weeks due to treatment-related toxicity, remove patient from study

decrease by one dose level. • If recurs again, reduce by one additional dose	
level.If recurs again, reduce by one additional dose level.	

Table 3B. Dose Modifications for non-Hematologic Toxicities. See Dose Levels for venetoclax and CC-486 in Table 4.

Observation	Action	Comments
AE resolves promptly with supportive care	Maintain dose level	
Febrile neutropenia or neutropenia with infection	 Withhold all agents until resolution of fever and infection (as applicable) 	
Grade 3 or higher non- hematologic AE that does not resolve to grade 2 or	 Hold venetoclax, CC- 486, and obinutuzumab (if applicable) 	Monitor CBC and CMP weekly.
below within one week despite maximum supportive care	• Resume therapy at same dose level once AE resolves to ≤ grade	No more than 3 dose reductions are allowed
	 If recurs, reduce by one dose level. If recurs again, reduce by one additional dose level. 	If treatment is delayed by more than 6 weeks due to treatment-related toxicity, remove patient from study
	If recurs again, reduce by one additional dose level	

Table 4. Venetoclax and CC-486 Dose Levels to be used if dose modifications are needed as per Tables 3A and 3B in the Expansion Cohort.

Agent	Starting Dose	Dose Reduction #1	Dose Reduction #2	Dose Reduction #3
Venetoclax	RP2D dose and schedule	RP2D dose on Days 1-10 only	50% reduction in dose, on Days 1-10 only	75% reduction in dose, on Days 1-10 only

and schedule same schedule same schedule with every other day dosing
--

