APPENDIX G: ELECTROLYTE IMBALANCES AND PREVENTION OF TUMOR LYSIS SYNDROME

Within the first 24 hours after the first dose or dose increase of any investigational agent in this protocol, if any laboratory criteria below are met, the patient should be hospitalized for monitoring and the investigator notified. No additional doses of investigational agents should be administered until resolution. Following resolution, investigational agents may be resumed following the dose modification guidelines in Section 4.2.2 and Section 4.2.3.

A rapidly rising serum potassium level is a medical emergency.

Guidelines for management are as follows:

- Nephrology (or acute dialysis service) must be consulted/contacted on admission (per institutional standards to ensure emergency dialysis is available).
- IV fluids (e.g., D5 1/2 normal saline) should be initiated at a rate of at least 1 mL/kg/h rounded to the nearest 10 mL (target 150 to 200 mL/h; not 50 mL/h). Modification of fluid rate should also be considered for individuals with specific medical needs.
- Monitor for symptoms or signs of TLS (e.g., fever, chills, tachycardia, nausea, vomiting, diarrhea, diaphoresis, hypotension, muscle aches, weakness, paresthesia, mental status changes, confusion, and seizures). If any clinical features are observed, recheck potassium, phosphorus, uric acid, calcium, and creatinine within 1 hour.
- Vital signs should be taken at time of all blood draws or any intervention.
- The management recommendations below focus on the minimum initial responses required. If a diagnosis of TLS is established, ongoing intensive monitoring and multi-disciplinary management will be per institutional protocols.

Specific recommendations:

Abnormality	Management Recommendations			
Hyperkalemia (including rapidly rising potassium)				
Potassium > 0.5 mmol/L increase from prior value (even if potassium within normal limits)	 Recheck potassium, phosphorus, uric acid, calcium, and creatinine in 1 hour. If further 0.2 mmol/L increase in potassium, but still upper limit of normal (ULN), manage per potassium ULN. Otherwise recheck in 1 hour. Resume per protocol testing if change in potassium is 0.2 mmol/L, and potassium ULN, and no other evidence of tumor lysis. At the discretion of the treating investigator, may recheck prior to hospitalization. If stable or decreased, and still WNL, hospitalization is at the 			

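### Section 7.4.1 has no attribution test for the acute kidney injury criterion of clinical TLS, so in the expansion cohort 4.2.3 calls for a venetoclax reduction after a creatinine rise from any cause

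*Combined protocol and SAP*

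**What the plan says.** Section 7.4.1 gives three clinical criteria for tumor lysis syndrome (TLS), covering 3 days before to 7 days after initial therapy, and says that "One of the following clinical criteria is sufficient to diagnose TLS". The first is "Cardiac dysrhythmia at least probably attributable to hyperkalemia". The second covers dysrhythmia, seizure, neuromuscular irritability, hypotension or heart failure, with the same degree of attribution to hypocalcemia. The third begins "Acute kidney injury, defined by increase in serum creatinine level > 0.3 mg/dL from baseline" and can also be met by a single high creatinine value or by low urine output. It carries no attribution wording, excludes no other cause and does not require laboratory TLS at the same time.

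For the expansion cohort, 4.2.3 sets the venetoclax action. Short laboratory-only TLS is exempt: "If TLS is diagnosed by laboratory criteria only AND resolves within 48 hours, venetoclax may be resumed at the prior dose without adjustment". Laboratory TLS lasting longer than 48 hours leads to a reduction. So does any clinical diagnosis: where "TLS is diagnosed by clinical criteria, the dose of venetoclax should be reduced following Table 4", no allowance is made for quick resolution. The first venetoclax step in Table 4 is "RP2D dose on Days 1-10 only".

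Table 3B in 4.2.5 is the general table for non-hematologic events in the same cohort. Where an "AE resolves promptly with supportive care", it keeps the dose level. Section 8.2.5 makes TLS of any grade an event of special interest whatever its cause.

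**The concern.** The two criteria with an attribution test ask whether the clinical event came from the metabolic disturbance of lysis. The kidney criterion asks only whether creatinine moved. A modest rise in the first week can come from volume loss, and the protocol expects the conditions for that: 7.4.12 lists vomiting and diarrhea among the common reactions to these drugs. It adds that azacitidine's gastrointestinal events fall mainly in the first two cycles and more often in the first week of a cycle, which overlaps the 7-day TLS window.

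What is at stake is dosing. An expansion patient with a short, explained creatinine rise that is not lysis would have venetoclax cut to a 10-day schedule by a rule meant for lysis. Two electrolyte abnormalities that clear within 48 hours would leave the dose unchanged.

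**Working it through.** The plan states no figure to reproduce. The check sets the sections side by side and adds short arithmetic.

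**1. Is the kidney criterion the only clinical one without attribution?** Yes. Criterion 1 requires a probable link to hyperkalemia and criterion 2 a probable link to hypocalcemia. Criterion 3 requires none. The laboratory criteria also carry no attribution wording, but they need two abnormalities within the same 24 hours and have the 48-hour exemption.

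**2. Can the trigger arise in routine follow-up?** Yes. Section 5.3.4 schedules a metabolic panel with creatinine on Cycle 1 Day 8, seven days after Day 1. The visit window in 5.3 is 3 days either way, so a sample taken on Days 5 to 8 falls inside the TLS window.

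**3. Worked example (creatinine values assumed).** Baseline 0.9 mg/dL, then 1.25 mg/dL on Day 5 after vomiting, resolving promptly with fluids:

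- Rise: 1.25 - 0.90 = 0.35 mg/dL, which is above 0.3.
- 7.4.1: clinical TLS, with no question asked about cause.
- 4.2.3: reduce venetoclax per Table 4. The 48-hour exemption does not apply because the diagnosis is clinical.

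**4. Size of the first reduction per cycle.**

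- RP2D on Days 1-28: 10/28 = 35.7% of dose-days remain, a cut of 18/28 = 64.3%.
- RP2D at DL -2, already Days 1-10: 10/10, no change.

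**5. Comparison with how other events are handled in the expansion cohort.**

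- Laboratory-only TLS resolving within 48 hours (4.2.3): same dose allowed.
- Event resolving promptly with supportive care (Table 3B): same dose.
- First grade 3 or higher non-hematologic event not improved to grade 2 or below within a week (Table 3B): hold, then resume at the same dose.
- Creatinine rise above 0.3 mg/dL in the TLS window, any cause and any duration (7.4.1 with 4.2.3): reduce.

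The last event can be the mildest of the four, yet it is the only one that leads to a reduction at first occurrence.

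**The case against.** **The broad criterion may be deliberate.** Section 7.4.1 says the TLS risk of the combination in follicular lymphoma is unknown and names compromised renal function and dehydration as risk factors. It credits the definition to a published guideline that was not available here, so the missing attribution test cannot be called a drafting slip. This stands for diagnosis and reporting, and is a reason to leave 7.4.1 alone. It does not explain why a cause known not to be lysis should reduce venetoclax.

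**Table 3B and 4.2.3 may not truly conflict.** A reader might infer a contradiction. The documents state no order of precedence, but 4.2.3 is specific to TLS and would ordinarily govern over a general table. Table 3B also keeps the dose only if the event resolves promptly. The concern is therefore what the governing rule does, not that two rules collide. Section 7.4.13 does not collide either: it concerns CC-486, and unexplained rises only.

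**The means to judge cause are not missing.** A reader might infer a work-up gap because Appendix G orders its chemistry panel "Within the first 24 hours after the first dose or dose increase of any investigational agent in this protocol", and 24 of 7 x 24 = 168 hours is 14%. Its creatinine trigger, a rise above 25%, is also harder to reach than 0.3 mg/dL once baseline exceeds 0.3/0.25 = 1.2 mg/dL. That inference is too strong. Appendix G also calls for the panel when clinical features such as vomiting appear. Section 7.4.1.1 refers patients with suggestive electrolyte changes to Appendix G without repeating the time limit, and leaves other post-dose tests to the investigator. The Day 8 visit already returns potassium, urea nitrogen and LDH with creatinine. The tests are available, though not mandated for the full window.

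**The loss may be short.** Section 4.2.3 lets the investigator return to the prior dose after unacceptable toxicity resolves, while 4.2.5 forbids re-escalation. A reader might infer a permanent reduction, but the documents do not settle this. It is a separate inconsistency, and nothing here relies on it.

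**Conclusion.** The point holds as a minor flaw in a dosing rule. As written, 7.4.1 and 4.2.3 together call for a venetoclax reduction in an expansion patient whose creatinine rises more than 0.3 mg/dL within 7 days after initial therapy, whatever the cause and however short the rise. Laboratory-only TLS that clears within 48 hours is spared.

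Per affected patient, each reduced cycle keeps 10 of 28 venetoclax dose-days, assuming a Days 1-28 RP2D and the first Table 4 step. If the RP2D is DL -2, that step has no effect. The documents give no kidney-injury rate, so the number affected cannot be estimated; at most the 32 planned expansion patients are exposed.

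A reader might infer that such reductions would lower the 6-month CR rate or distort the Simon test. The documents do not support that: TLS is not an endpoint, and neither the frequency nor the duration of such reductions can be derived from them. This is not an analysis choice.

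**What to change.** Add one clause to 4.2.3. When clinical TLS rests on the kidney criterion alone, venetoclax is reduced only if the investigator judges the injury at least probably attributable to tumor lysis. Creatinine is compared with the pre-dose value, which 7.4.1.1 already uses as the reference for TLS changes. State that Table 3B governs otherwise, and that 7.4.13 applies to CC-486 if the rise is unexplained. Do not require an electrolyte abnormality, so that lysis can still be called when samples are missing. Leave 7.4.1 and 8.2.5 unchanged, so no AESI or SAE report is lost.

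Do not extend the Appendix G creatinine trigger to 7 days. Its preamble ties the listed criteria to hospitalization and a hold on all study drugs. A rise from 0.60 to 0.76 mg/dL (0.16/0.60 = 27%) on Day 6, which is not TLS by the 0.3 mg/dL test, could then mean admission. At most, recommend outside Appendix G a same-day potassium, phosphorus, uric acid and calcium check when creatinine rises more than 0.3 mg/dL in the 7-day window, without mandatory admission or hold.

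The cost is one clause and, if adopted, an occasional extra blood draw. The downside is added investigator judgement, which could occasionally miss a warranted reduction, and a TLS test for dosing that is narrower than the one for reporting. Section 4.2.5 says the expansion dose-modification text is open to revision after phase I, and 6.2.2 already plans a review before that cohort starts, so it can be settled then.

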7.4.1.1 TLS Prophylaxis

In the dose-finding cohort, all patients must receive prophylaxis for TLS before the initiation of the first dose of combination therapy with venetoclax and obinutuzumab on Cycle 1 Day 1.

In the expansion cohort, all patients must receive prophylaxis for TLS prior to venetoclax administration on cycle 1 day 1. Those with high tumor burden, high circulating absolute lymphocyte counts ($> 25 \times 109$ /L), or renal impairment are considered at risk for TLS and must receive

prophylaxis prior to initiation of obinutuzumab on Cycle 4 Day 1 if they are not already on appropriate TLS prophylaxis. For subjects enrolled in the expansion cohort who do not meet those criteria at the time of initiation of obinutuzumab, the need for TLS prophylaxis will be left to the clinical judgement of the treating investigator.

Prophylaxis will include the following:

- Appropriate hydration, consisting of a fluid intake of approximately 2 to 3 L/day starting 24 to 48 hours before the start of treatment.
- Administration of an agent to reduce uric acid (such as allopurinol 300 mg/day orally beginning 72 hours before dose and continuing for 37 days afterwards) or rasburicase IV (for those high risk patients with elevated uric acid levels before treatment, or when otherwise judged to be appropriate by the treating investigator) until normalization of serum uric acid and other laboratory evidence of TLS (e.g., elevated serum LDH levels). Patients with an allergy to allopurinol should receive an alternative TLS prophylaxis regimen such as febuxostat.
- Laboratory results should be reviewed and electrolyte values should not demonstrate any clinically significant abnormalities before the first dose of venetoclax or obinutuzumab, or the patient should receive additional prophylactic treatment and hydration before the initiation of dosing.

On the day of the first administration of venetoclax and/or obinutuzumab, serial vital signs will be measured, and serum chemistry and hematology samples will be drawn before venetoclax and/or obinutuzumab dosing (see Appendix A). These samples are to be sent immediately to the laboratory and the treating investigator or designee must review the results promptly. Laboratory values obtained before the dose of venetoclax and/or obinutuzumab are to be used to determine whether a patient developed a change related to TLS. Additional laboratory studies including post-dose studies are up to the judgement of the treating investigator but are not required by the study protocol. Patients who develop electrolyte changes suggestive of TLS should undergo aggressive management and further monitoring per Appendix G.

